5.1 Imputation rules

5.1.1 Study drug

The study drug administration date should be complete since it's taken in the hospital. In case missing or partial, the visit date will be used as the study drug administration date.

5.1.2 AE date imputation

The following missing dates will not be imputed

- Missing AE start dates
- AE start dates missing the year
- Partial/missing AE end dates

For other type of partial missing start dates, rules specified in [Tables 5-1](#) to [Table 5-3](#) will be used

Table 5-1 AE/Treatment Date Abbreviations

	Day	Month	Year
Partial Adverse Event Start Date	<not used>	AEM	AEY

	Day	Month	Year
Treatment Start Date (TRTSTD)	<not used>	TRTM	TRTY

Table 5-2 describes the possible combinations and their associated imputations. The upper text indicates the imputation (NC, A, B, C etc.) and the lower text the relationship of the AE start date to the treatment start date (TRTSTD).

Table 5-2 Imputation algorithm

	AEM MISSING	AEM < TRTM	AEM = TRTM	AEM > TRTM
AEY MISSING	NC Uncertain	NC Uncertain	NC Uncertain	NC Uncertain
AEY < TRTY	(D) Before TRTSTD	(C) Before TRTSTD	(C) Before TRTSTD	(C) Before TRTSTD
AEY = TRTY	(B) Uncertain	(C) Before TRTSTD	(B) Uncertain	(A) After TRTSTD
AEY > TRTY	(E) After TRTSTD	(A) After TRTSTD	(A) After TRTSTD	(A) After TRTSTD

The legend to the above table is shown in Table 5-3.

Table 5-3 Imputation algorithm legends

Relationship		
TRTSTD	Before	Indicates AE start date prior to Treatment Start Date
	After	Indicates AE start date after Treatment Start Date
	Uncertain	Insufficient to determine the relationship of AE start date to Treatment Start Date
Imputation calculation		
Blank	NC /	No convention/imputation
	(A)	01MONYYYY
	(B)	TRTSTD+1
	(C)	15MONYYYY
	(D)	01JULYYYY
	(E)	01JANYYYY

Few examples are shown in Table 5-4.

Table 5-4 Example scenarios

Partial AE start date	Treatment start date	Relationship with TRTSTD	Imputation Calculation	Imputed Date
12mmyyyy	20OCT2001	Uncertain	NC	<blank>
ddmmm2000	20OCT2001	Before	(D)	01JUL2000
ddmmm2002	20OCT2001	After	(E)	01JAN2002

Partial AE start date	Treatment start date	Relationship with TRTSTD	Imputation Calculation	Imputed Date
ddmmm2001	20OCT2001	Uncertain	(B)	21OCT2001
ddSEP2001	20OCT2001	Before	(C)	15SEP2001
ddOCT2001	20OCT2001	Uncertain	(B)	21OCT2001
ddNOV2001	20OCT2001	After	(A)	01NOV2001

5.1.3 Concomitant medication/non-drug therapy date imputation

Missing concomitant dates will be imputed similar as to AE dates.

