2.1.1 General definitions

Study treatment: KAF156, Lumefantrine solid dispersion formulation (LUM-SDF) are part of investigation treatments. Coartem® is used as standard of care (SOC). They are referred to as study treatments in the document.

Treatment group name will be used in statistical analyses and outputs. Abbreviated treatment group description that concatenates drug code, dosage, no. of doses, and food intake in the form of “KAFxxxmg/LUMyyyymg- QD x X food intake” will be used as the column headers in the CSR outputs. If all the treatment groups are not accommodated within a page of a post text table, the names may be shortened such as by deleting the unit “mg”.

For example, the initial treatment groups in Run-in Cohort will be displayed as:

- KAF400mg/LUM240mg- QDx2-Fed
- KAF400mg/LUM240mg-QDx2-Fasted

As per study design, other dose combinations of KAF/LUM with different food recommendation may also be used. It is also possible to use treatment for 3 days. Treatment groups for each of the combinations will be used accordingly.

Baseline: The last measurement made prior to administration of the first dose of study treatment. Note this may include measurements taken on the day of randomization (e.g. lab, ECG, vitals).

If a patient did not receive any dose of study treatment then the randomization date will be used as the date of first dose of study treatment.

Study day: Study day will be calculated with respect to the first dose of study treatment. The first day of administration of study treatment (first dose) is defined as Day 1. Day -1 will be the day before Day 1. Day 0 does not exist. Due to the multiple assessments collected more than once for a day in the treatment phase for some variables, the study day calculation is based on the treatment start date and time.

For the assessments that are performed more than once for a day:

$\text{Study day} = \text{Integer}(\text{datetime of assessment} - \text{datetime of first dose of study treatment}) / (60 * 60 * 24) + 1.$

For assessments that are performed once for a day: study day = date of assessment – date of first dose of study treatment + 1.

For assessments collected prior to Day 1, study day = date of assessment - date of first dose of study treatment.

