2.1.1.1 Definition of treatment failures

Early Treatment Failures (ETF)

Patient will be classified as ETF upon meeting any of the following criterion

- Development of danger signs or severe malaria on Day 2, Day 3, Day 4 in the presence of parasitaemia.
- Parasitaemia on Day 3 higher than Day 1 count irrespective of axillary temperature.
- Parasitaemia on Day 4 with axillary temperature $\geq 37.5^{\circ}\text{C}$.
- Parasitaemia on Day 4 equals to or more than 25% of count on Day 1.

Late Clinical Failure (LCF)

Patient will be classified as LCF upon meeting any of the following criterion

- Development of danger signs or severe malaria on any day from Day 5 to Day 43 in the presence of parasitaemia without previously meeting any of the criteria of early treatment failure.
- Presence of parasitaemia and axillary temperature $\geq 37.5^{\circ}\text{C}$ on any day from Day 5 to Day 43 without previously meeting any of the criteria of Early Treatment Failure.
- Missing body temperature assessment in presence of parasitemia will be classified as LCF.

Late Parasitological Failure (LPF)

- Presence of parasitaemia on any day from Day 8 to Day 43 and axillary temperature $< 37.5^{\circ}\text{C}$ without previously meeting any of the criteria of Early Treatment Failure or Late Clinical Failure.

Note: If the temperature is measured using other routes, such as oral/tympanic/rectal, the corresponding threshold for fever is 38.0°C . Danger signs or severe malaria is recorded as adverse events. The adverse event start date of danger signs or severe malaria will be used in the determination of ETF and LCF. Only *P. Falciparum* asexual form is used for parasitaemia/parasite in the assessments of treatment failure and ACPR in [Section 2.1.1.2](#) below. The body temperature assessment closest to the blood smear assessment date will be used.

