2.1.1.2 Definition of ACPRs

Uncorrected ACPR at Day X where X=15, 29, or 43

- A patient is considered as non-responder at Day X if the patient experiences an ETF, LCF from Day 5 to Day X, or LPF from Day 8 to Day X.
- A patient is also considered as non-responder if the parasite is not cleared by Day X unless the patient discontinues the study prior to Day X without ETF or LCF or LPF, in which case the response is considered as missing. Note that if a patient takes non-study antimalaria medications during the treatment period, the patient is considered as non-responder.

- A patient is considered as responder (Uncorrected ACPR) at Day X if the patient is not classified as a non-responder at Day X and the patient has a malaria blood film showing absence of parasite at Day X or later if Day X is missing.
- The response for a patient is considered as missing/undetermined if the patient is not classified as a non-responder prior to Day X and the malaria blood film result at Day X is missing and not followed by a subsequent negative result.

PCR-corrected ACPR at Day X where X=15, 29, or 43

- A patient is considered as non-responder at Day X if the patient experiences an ETF or LCF from Day 5 to Day 7.
- A patient is also considered as non-responder if the initial parasite is not cleared by Day X unless the patient discontinues the study prior to Day X without ETF or LCF or LPF, in which case the response is considered as missing. Note that if a patient takes non-study antimalaria medications during the treatment period, the patient is considered as non-responder.
- A patient is considered as non-responder at Day X if the patient has a parasite recrudescence from Day 8 to Day X
- A patient is considered as responder (corrected ACPR) at Day X if the patient is not classified as a non-responder by Day 7 and has negative results at Day X based on microscopy and PCR genotyping.
- A patient is considered as responder at Day X if the patient is not classified as a non-responder at Day X and the patient has a malaria blood film showing absence of parasite at Day X or later if Day X is missing.
- A patient is considered as responder at Day X if the patient is not classified as a non-responder at Day X and the patient has a malaria blood film showing new infection **at** Day X using PCR genotyping or later if Day X is missing.
- The response for a patient is considered as missing/undetermined (e.g., due to missing PCR data or miss blood smear data) if

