5.8 Rule of exclusion criteria of analysis sets

Table 5-14 Protocol deviations and non-PD criteria leading to exclusion from analysis sets

Analysis Set	PD (Description and ID) that causes Patients to be excluded	Non-PD criteria that cause Patients to be excluded
Randomized	
 Informed Consent for study participation or parental consent not obtained and patient entered trial (INCL05) 	
 Not randomized Misrandomized if identified from IRT
FAS	NA	
 Not in Randomized set Baseline parasitaemia count is 0 or missing No study drug taken
PPS	
 Parasite specie is other than Plasmodium falciparum OR mixed infection (INCL03) Baseline plasmodium falciparum parasite count <1000/uL or ≥150000/uL (INCL04) at the time of prescreening for the Run-in; plasmodium falciparum parasite count < 1,500 or ≥ 150,000 /uL parasites/μL at the time of pre-screening for Cohorts 1 and 2 No fever within the past 24 hours at baseline (INCL06) Prohibited non-antimalarial medications that may have effect on efficacy if received before the Day 29 visit without being falciparum treatment failures (COMD001A) Only for Run-in Cohort, do not fully comply with the food guidelines according to randomization (with OTH04 either day) 	
 Not in FAS; <80% of randomized study medication taken Received non-study concomitant antimalarial drugs during the treatment period Received non-study concomitant antimalarial drugs after the treatment period between Day 4 and Day 29 without experiencing treatment failure Not classified as non-responder before Day 8, no positive blood smear parasite on Day 8 onwards, and blood smear parasite result is missing at Day 29 and later (early discontinued) Not classified as non-responder before Day 8, have at least one positive blood smear parasite result between Day 8 and Day 29 which cannot be determined as recrudescent or new infection based on PCR genotyping and have parasites cleared prior to the positive blood smear parasite; Not classified as non-responder before Day 8, have a new infection prior to study Day 27 and have

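### The AE start-date imputation is also used for antimalarials and danger signs, so a partial date can move a later event into the treatment or early-failure window and change primary status or PPS membership

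*SAP*

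**What the plan says.** SAP 5.1.3 is one sentence: "Missing concomitant dates will be imputed similar as to AE dates". It makes no exception for antimalarials, and 5.1.3.1 on other imputations is marked not applicable. The AE algorithm (5.1.2, Tables 5-2 and 5-3) has two branches that matter here:

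- Rule B: month of first dose with the day missing, or only the year known and equal to the treatment year. The start becomes first dose + 1. The SAP labels this situation "Insufficient to determine the relationship of AE start date to Treatment Start Date".
- Rule A: a later month with the day missing. The start becomes the 1st of that month.

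Wholly missing dates and "AE start dates missing the year" are left blank.

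Three efficacy rules read the resulting dates:

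- SAP 2.1.1.1: "The adverse event start date of danger signs or severe malaria will be used in the determination of ETF and LCF". One ETF criterion is "Development of danger signs or severe malaria on Day 2, Day 3, Day 4 in the presence of parasitaemia".
- SAP 2.1.1.2: "if a patient takes non-study antimalaria medications during the treatment period, the patient is considered as non-responder". Table 5-13, criterion 6, repeats this for the full-set analysis and excludes the child from the PPS.
- SAP 5.8, Table 5-14, lists as a PPS exclusion "Received non-study concomitant antimalarial drugs during the treatment period". A second row excludes antimalarial use from Day 4 to Day 29, but only where no treatment failure occurred.

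SAP 2.7.2.4 also censors PCT and FCT at first antimalarial use. Its own imputation covers the clock time, not the date. The primary test uses the PPS (2.5.2).

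**The concern.** For a safety table, an early imputed date is the cautious choice because it keeps an event in the treatment-emergent count. For efficacy it is not cautious. It moves the event to the day on which the antimalarial and ETF rules have their strongest effect. Children are in hospital to Day 4 (Protocol Section 3), where dates are well observed, so a partial date most plausibly belongs to something that happened after discharge. Day 2 is then one of the least likely true dates.

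At stake are a child's PCR-corrected status, membership of the set on which non-inferiority is tested, the split between ETF and LCF, and the censoring times for PCT and FCT. The error can help or hurt either arm.

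**Working it through.** **1. The rule reproduces the SAP's examples.** Coding Tables 5-2 and 5-3 gives all seven rows of Table 5-4. With first dose 20 Oct 2001, for example, an October date without day becomes 21 Oct and a November date without day becomes 1 Nov.

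**2. Study days.** "The first day of administration of study treatment (first dose) is defined as Day 1", so study day = date − first-dose date + 1.

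- Rule B always gives Day 2. This is inside the treatment period (the comparator runs three days, and the post-treatment row of Table 5-14 starts at Day 4) and inside the ETF window.
- Rule A gives Day 2, 3 or 4 only when first dose falls on the last, second-last or third-last day of a month. Otherwise it backdates to Day 5 or later.

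**3. How often, given that a partial date exists.** Assumption: first doses are uniform over a 365-day year and only the day is missing. For an event truly on Day d (d ≤ 29), rule B applies to 365 − 12(d − 1) first-dose dates. Rule A adds the last two days of each month (24 dates) if we count Day 3 or earlier, or the last three (36 dates) if we count Days 2–4.

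| True day | Rule B | Day 3 or earlier | Days 2–4 | Mean backdating |
|---|---|---|---|---|
| 8 | 281 | 305/365 = 84% | 317/365 = 87% | 5.3 days |
| 15 | 197 | 221/365 = 61% | 233/365 = 64% | 10.0 days |
| 29 | 29 | 53/365 = 15% | 65/365 = 18% | 14.6 days |

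The imputed date is before the true one in 97% of cases. In the other 3% the event truly fell on the 1st of a later month. For true Days 35 and 43 nothing reaches Days 2–4, but 77% and 51% are imputed before Day 29.

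**4. Which cases change the primary PPS analysis.**

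- (a) First dose 1 Oct, new infection at the Day 29 visit (29 Oct), rescue dated October without day. The true outcome is PPS responder (2.2 criterion e; Table 5-13, criterion 8). Rescue is imputed to 2 Oct = Day 2, so the child is excluded, or a non-responder if the Table 5-13 worst-case note governs.
- (b) First dose 3 Oct, recrudescence on Day 15 (17 Oct), rescue dated October without day. The true outcome is PPS failure. With rescue on Day 2 the child meets the treatment-period exclusion in Table 5-14, which lacks the treatment-failure exemption given in 2.2. The worst-case note says non-responder instead. The SAP does not say which prevails.
- (c) First dose 3 Oct, danger sign on Day 20 (22 Oct) with a negative film or a new infection, dated October without day. The true outcome is responder, or PPS exclusion for a new infection before Day 27. Imputed to Day 2, with parasites still present then, it is scored ETF and enters the PPS as a failure (2.2 criterion a).
- (d) First dose 20 Oct, non-rescue antimalarial on 23 Nov (Day 35), dated November without day. It is imputed to 1 Nov = Day 13, and the child is excluded from the PPS although the drug followed the Day 29 assessment.

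**5. Size per child.** The plan's power reproduces: Φ(0.10/√(2 × 0.95 × 0.05/92) − 1.96) = 87.5%, against at least 87% stated. Take control at 87/92. The lower 95% limits for the difference are below. The unstratified Wald limit approximates the Mantel-Haenszel one; Newcombe is the Wilson uncorrected method.

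| Test arm | Wald | Newcombe |
|---|---|---|
| 87/92 | −6.6% | −7.4% |
| 86/92 | −7.9% | −8.7% |
| 85/92 | −9.3% | −10.1% |
| 84/92 | −10.7% | −11.4% |
| 84/91 (one true failure dropped) | −9.4% | −10.2% |

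One responder turned into a failure costs about 1.4 points; from 85/92 to 84/92 the Wald limit crosses −10%. Dropping one true failure moves it back, from −10.7% to −9.4%. Dropping one responder hardly matters: 86/91 gives −6.6%, a change of about 0.1 point.

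**The case against.** The strongest reply is that partial dates on these records should be rare. A film and a genotyping sample precede rescue, safety bloods are taken on the first day of rescue, and adherence is followed for three days (Protocol 6.2.3). Rescue has its own category (SAP 2.4.2). Missing values are queried, and data for the primary variables are fully source-verified (Protocol 11.2, 11.3). All this stands. It means that the percentages above are conditional on a partial date existing, and that no expected effect on the trial result can be stated.

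A reader might also infer more than the documents support:

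- That a Day 15 new infection with a backdated rescue changes the primary result. It does not. That child is already outside the PPS (2.7.2.1; Table 5-13, criterion 9; Table 5-14). Only the FAS run that counts new infections as responders changes, and the Kaplan-Meier analysis, where the child becomes an event instead of being censored.
- That every backdated danger sign changes primary status. A recrudescence is a non-responder either way, and only its ETF or LCF label moves. Case (c) also needs parasitaemia on Days 2–4.
- That a drug stopped before dosing turns from prior to concomitant. Prior use is defined by stopping before first dose (2.4.2), so the class holds. The imputed start would merely fall after the known end.
- That the shift is always earlier. It is not in the 3% above, and a pre-dose start in the month of first dose moves forward to Day 2.

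**Conclusion.** The point holds in limited form. A stated rule, not a gap, assigns dates that are implausible for post-discharge events to rules that decide primary status and PPS membership, and nothing else in the SAP overrides it. The primary PPS analysis is exposed in cases (a) to (d). Case (b) also reveals a separate inconsistency between 2.2, Table 5-14 and the Table 5-13 note, which should be settled in any event.

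Per affected child the lower limit moves by up to about 1.4 points in either direction, which matters only if the result lies close to −10%. This rests on the planned 92 per group, 95% response in the control arm, and uniform first-dose dates. The frequency of partial dates is not in the documents and is probably small, so this is a minor-to-moderate correction to make before lock.

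**What to change.** Keep the AE rule for safety tables only. In 5.1.3 and 2.1.1.1 add a date rule for efficacy, PPS and PCT/FCT derivations:

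- Partially dated rescue antimalarial: the date of the positive film or failure visit that led to it, or of the last vomited study dose if given for repeated vomiting.
- Partially dated non-rescue antimalarial: the visit at which it was first recorded, within the bounds of the known month and end date.
- Danger signs or severe malaria: the visit or film at which they were recorded.
- No imputed start may fall after a known end date.

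Align the treatment-period row of Table 5-14 with the treatment-failure exemption in 2.2, and say whether exclusion or the worst-case note prevails. Resolve any remaining partial date that affects primary status by query or treatment-blind review before database lock.

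The cost is SAP wording, a small programming change and some date queries. Sample size and power are unaffected.

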5.1.3.1 Other imputations

NA

5.1.4 Visit windows

When visit windows are used, all visits will be re-aligned, i.e., they will be mapped into one of the visit windows. E.g., if the Day 4 visit of a patient is delayed and occurs on Day 7, say, it will be re-aligned to visit window Day 8. In the case of major deviations from the visit schedule, or due to unscheduled visits, several assessments of a patient may fall in a particular visit window (either scheduled or unscheduled). Statistical approaches to handle multiple assessments in a given visit window are specified below.

- Of note, patients are allowed to have gaps in visits. All data collected will be displayed in listings.
- Lower limit and upper limit of the Day 29 visit is set to be Day 27 and Day 33 respectively, with narrow window since this is the primary analysis timepoint.
- The following rules are used to determine the window for other visits post baseline:
 - “Lower limit” = “upper limit of prior applicable visit” + 1.
 - “Upper limit” = “target day of current visit” + integer part of (“target day of next applicable visit” – “target day of current visit”)/2 with the exception of Day 29
 - No upper limit for Day 43 visit
 - Upper limit of Day 15 is one day before the lower limit of Day 29

For assessments that are scheduled to be performed only once on a day, [Table 5-5](#) describes the analysis windows mapping to visits (not just scheduled visits) based on study days alone. For the assessments that may be performed on multiple timepoints on a day, [Table 5-6](#) describes the analysis windows mapping to visits based on study day and time. Repeat and/or unscheduled visits (which will be numbered in the database according to new NCDS standards) will be mapped for analysis purposes in the same way. If there are multiple measurements within an analysis window, the conventions defined in [Table 5-7](#) will be used to determine the appropriate measurement to be selected for analysis.

The mapped visits will be used in the by visit analyses. However, the listings will show all collected data regardless of used in the by visit analyses.

Table 5-5 Analysis visit windows based on study days alone

Analysis Visit	Target Day	Analysis window for assessment group		
		Vital signs/ Chemistry/ Hematology/ Urinalysis	Thyroid function	
Baseline	1	Up to Day 1	Up to Day 1	
Day 2	2	Day 2	NA	
Day 3	3	Day 3	NA	
Day 4	4	Day 4	NA	
Day 5	5	Day 5 - 6	NA	
Day 8	8	Day 7 - 11	NA	
Day 15	15	Day 12 - 26	Day 2 - 29	
Day 29	29	Day 27 - 33	NA	
Day 43/End of study	43	Day 34 and above	Day 30 and above	

Table 5-6 Analysis visit windows based on study day and time

Analysis Visit	Analysis timepoint	Analysis window for assessment group			
		Parasite count/Temperature*	ECG	PK (Run-in)	PK (Cohorts 1&2)
Baseline	0 hrs	up to 0 hrs	up to 0 hrs	up to 0 hrs	up to 0 hrs
Day 1	1 hrs	NA	NA	> 0 - 2 hrs	NA
	3 hrs	NA	>0 – 4.5 hrs	> 2 – 3.5 hrs	>0 – 4.5 hrs
	4 hrs	NA	NA	>3.5 – 4.5 hrs	NA
	5 hrs	NA	NA	>4.5 – 5.5 hrs	NA
	6 hrs	>0 - 9 hrs	>4.5 - 15 hrs	>5.5 - 7 hrs	>4.5 – 15 hrs
	8 hrs	NA	NA	>7 – 16 hrs	NA
	12 hrs	>9 - 18 hrs	NA	NA	NA
Day 2	24 hrs	>18 hrs to 33 hrs	>15 – 25.5 hrs	>16 – 24.5 hrs	>15 – 25.5 hrs
	25 hrs	NA	NA	>24.5 – 26 hrs	NA
	27 hrs	NA	>25.5 – 28.5 hrs	>26 - 27.5 hrs	>25.5 – 28.5 hrs
	28 hrs	NA	NA	>27.5 – 28.5 hrs	NA
	29 hrs	NA	NA	>28.5 – 29.5 hrs	NA
	30 hrs	NA	>28.5 - 39 hrs	>29.5 - 31 hrs	>28.5 – 39 hrs
	32 hrs	NA	NA	>31 - 40 hrs	NA
	36 hrs	>33 – 42 hrs	NA	NA	NA
Day 3	48 hrs	>42 – 60 hrs	>39 – 49.5 hrs	>40 – 60 hrs	>39 – 60 hrs
Day 4	51 hrs	NA	>49.5 - 52.5 hrs	NA	>49.5 - 52.5 hrs
	54 hrs	NA	>52.5 – 61 hrs	NA	>52.5 – 61 hrs
	68 hrs	NA	>61 – 70 hrs	NA	>61 – 70 hrs
	72 hrs	>60 hrs to Day 4	>70 hrs to Day 5	>60 – 120 hrs	> 60 hrs
Day 5	NA	Day 5 - 6	NA	NA	NA
Day 8	168 hrs	Day 7 – 11	Day 6 -25	>120 hrs	NA

Day 15	NA	Day 12 - 26	NA	NA	NA
Day 29	NA	Day 27 - 33	NA	NA	NA
Day 43/End of study	NA	Day 34 and above	Day 26 and above	NA	NA

*Temperature should be checked every 6 hours until no fever. Since temperature is used for treatment failure also, the same window of parasite count is used.

Table 5-7 Rules for flagging variables

Timing of measurement	Type of data	Rule
Baseline	All data	The last measurement made prior to administration of the first dose of study treatment – note this may include measurements taken on the day of randomization. If a patient did not receive any dose of study treatment, then the randomization date will be used.
Post-baseline efficacy	parasite count and temperature	The measurement closest to the target day/time will be used. In the event two measurements are taken equally apart, the first one will be used.
Post-baseline safety	Summary visit information (e.g., lab, ECG, etc.)	The measurement closest to the target day/time will be used. In the event two measurements are taken equally apart, the first one will be used. If ECG is repeated, the higher value (worse case) of average triplicate between the scheduled and the repeated will be used for each measurement. Note, in such situations, the value used for analysis may be from the scheduled visit for some measurements but from repeated visit for other measurements.
Post-baseline safety	Notable abnormalities (e.g., lab, ECG, VS)	The most extreme measurement in the window will be used. Note this means a patient can have a notably high and notably low measurement within a window

